## DATA COLLECTION

Clinical data will be collected begin at time of consent from the patients' medical record as well as the administered questionnaires. All data obtained for this investigation will be entered and maintained into electronic case report forms via REDCap database. Clinical data collection will include subject demographics (age, gender, race/ethnicity), current medications, and medical history relevant to cancer risk such as smoking history, body mass index, and family history of cancer. In addition, we will collect clinically variables resulting from the CDDU exam (see primary endpoint). The participant questionnaire responses will also be entered. Follow-up data collection for outcomes on all participants will be performed at 3-4 months after the last treatment was given.

All data will be entered by approved study staff. Continuous data queries will be performed to ensure data integrity and completion.

**Resources:** *Describe the available resources to conduct the research (personnel, time, facilities, mentor commitment, etc.):* This proposal will require collaborative efforts between the Department of Urology and Clinical Studies Unit. For this proposal we will utilize the existing research infrastructure nestled within the Department of Urology. A clinical research coordinator will assist in screening, consenting, and enrollment and follow-up data and AE collection for all participating patients. Our Urology Senior Program Coordinator will

provide oversight and management to ensure timely and on budget study completion. Staff from the Urology Department will administer MoreNova shockwave therapy.

### FUNDING

For this proposal we are requesting funding through the Florida Comprehensive Focus Research Team for a total of **\$36,969.60**. Below is a breakdown of the approximated expected costs.

- Color Duplex Doppler Ultrasound (CDDU): ~\$728.48 per exam x 2 research exams per participant= \$1,456.92 per participant x 10 total enrolled= **\$14,569.60**
- Return Level 3 Office Visit: ~\$250 per visit x 6 visits= \$750.00 per participant x 10 total enrollment= **\$7,500**
- Clinical Research Coordinator (CCRC) .10 FTE for 1.5 years= ~**\$10,016**
- Clinical Research Assistant .10 FTE for 1.5 years= ~**\$4,884**

*To note, these are estimated costs and may not be reflective of true coordinator and data entry support.*

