#### PARTICIPATION

Once consented, the participants' medical history will be reported and a physical examination will be performed as part of standard of care. Participants will be asked to stop all PDE-5 inhibitors or injectable vascular stimulants for 1 week prior to first treatment (washout period) and throughout the treatments. The participant will then be scheduled to receive their first shock wave therapy via the MoreNova device. Participants will receive a total of 6 treatments lasting approximately 20 minutes each, two treatments weekly for 3 weeks. A CDDU diagnostic will

be reviewed in clinical records (within 12 months prior to study enrollment). CDDU will be repeated as part of the study at the final treatment and at the 3-4-month follow-up. Below is test schedule for study participants.

	Baseline	Treatment 1-5	Treatment 6	Follow-Up 1 month	Follow-up 3-4 month
Level 4 Evaluation/Consult H&E	X a				
Return Physical (Level 2 Return)		X	X		
Washout period		X b	X	X	
MoreNova Therapy		X	X		
Color Duplex Doppler Ultrasound (CDDU) Exam	X a		X		X
Questionnaires c	X a		X a	X a	X a
Adverse Events		X	X	X	X
Concomitant Medications	X	X	X	X	X

astandard of care

bBegin one-week **prior** to treatment 1

cIIEF-EF, EHS, SEP 2+3, and GAQ

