### Subject Information

*Target accrual is the proposed total number of subjects to be included in this study at Mayo Clinic. A "Subject" may include medical records, images, or specimens generated at Mayo Clinic and/or received from external sources.*

Target accrual: 10

Subject population (children, adults, groups): Participants will be men only requiring treatment for ED and following the inclusion/exclusion criteria below.

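### Does the office-visit budget line, whose printed factors give twice its stated product, call for a change to the plan?

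*Protocol*

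**What the plan says.** In the Funding section, the protocol states that "we are requesting funding through the Florida Comprehensive Focus Research Team for a total of" $36,969.60 and breaks the sum into four lines: ultrasound exams, office visits, a coordinator and a research assistant. The office-visit line is headed "Return Level 3 Office Visit". It takes about $250 "per visit x 6 visits", states $750.00, and then multiplies this "per participant x 10 total enrollment" to reach $7,500.

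The Participation section gives the visit count: "Participants will receive a total of 6 treatments lasting approximately 20 minutes each, two treatments weekly for 3 weeks". Its test schedule has a row "Return Physical (Level 2 Return)", marked at Treatments 1-5 and at Treatment 6, which makes six return visits per man. The Subject Information section sets the number of men: "Target accrual: 10".

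**The concern.** A reader who multiplies $250 by 6 gets twice the printed amount, and the tilde before $250 cannot explain a factor of two. The wrong product also reaches the requested total. The return visits carry no standard-of-care footnote in the schedule, so on the document's own marking they are study costs, and the protocol names no other funding source. At $250 each, $7,500 pays for 30 of the 60 planned treatment visits.

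If the request really were a fifth too low, one could fear that visits would be dropped or fewer men treated. In a study of 10 men, each man lost is 10% of the sample. The difference in visit level between the budget and the schedule adds to the impression of a cost basis that was not checked.

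**Working it through.** **Inputs.** From Funding: $728.48 per exam "per exam x 2 research exams per participant", with a line total of $14,569.60; about $250 per visit, 6 visits, with a line total of $7,500; coordinator $10,016; assistant $4,884; request $36,969.60. From Participation: 6 treatments, with a return physical at each. From Subject Information: 10 men.

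**Step 1, the stated total.** 14,569.60 + 7,500 + 10,016 + 4,884 = 36,969.60. This matches the request exactly, so $7,500 is the figure that was carried forward.

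**Step 2, the visit line from its printed factors.** 250 × 6 = 1,500 per participant; 1,500 × 10 = 15,000. The printed 750 and 7,500 are exactly half.

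**Step 3, the total if rate and count are right.** 14,569.60 + 15,000 + 10,016 + 4,884 = 44,469.60. The difference is 44,469.60 − 36,969.60 = 7,500, and 7,500 / 36,969.60 = 20.3%.

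**Step 4, which printed number is wrong?** Three readings are possible:

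| Reading | Rate | Visits | Per participant | For 10 | Total |
|---|---|---|---|---|---|
| Product wrong | $250 | 6 | $1,500 | $15,000 | $44,469.60 |
| Rate wrong | $125 | 6 | $750 | $7,500 | $36,969.60 |
| Count wrong | $250 | 3 | $750 | $7,500 | $36,969.60 |

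The $125 and the 3 are assumptions, since neither is printed in the protocol. The schedule supports 6 visits, which counts against the third reading. No other section gives the $250, and the conflict between Level 3 in Funding and Level 2 in the schedule leaves the unit price open. The document does not decide between the first two readings.

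**Step 5, a neighbouring line.** 728.48 × 2 = 1,456.96, whereas the protocol prints $1,456.92. The line total is nevertheless right: 1,456.96 × 10 = 14,569.60. So in this same section an intermediate figure is misprinted while the total stands. This does not show that $7,500 is right, but it means one cannot take the factors as right and the total as wrong.

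**Step 6, does the line pay for endpoint data?** The primary endpoint rests on the ultrasound exam. Baseline is the clinical exam already on record, and the two study exams (final treatment and 3-4 months) are budgeted in their own line. The questionnaires behind the secondary endpoint are marked standard of care at every time point. The disputed line prices return office visits only.

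**The case for a change.** The strongest case for acting is that the error is visible on the page and needs no outside source. It feeds the requested amount, and on every reading at least one printed number is wrong. The note that costs are estimates speaks of coordinator and data-entry support and does not excuse a product that contradicts its own factors. The Resources paragraph also promises completion on budget, which sits badly with a request that may be a fifth below its stated cost basis.

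The inconsistency stands in full. What does not stand is the step from there to lost data. No section makes visits or accrual conditional on this award. The Resources paragraph says that the study will use infrastructure already in place in the department and that department staff will give the treatments. The amount missing, if any, depends on a rate that the document leaves uncertain. Skipped visits or fewer men would be conjecture.

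**Conclusion.** The office-visit line does not multiply out: the printed factors give $1,500 per man and $15,000 for 10, against a stated $750 and $7,500. A shortfall of $7,500 (20.3% of the request) follows only if both the $250 rate and the six visits are right. The count is supported by the schedule and the rate is not. If the rate is the misprint, the request of $36,969.60 stands.

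This is a clerical slip in a cost estimate. Whoever administers the budget can reconcile the rate, count, product and visit level from the institution's fee schedule, without touching the design. The schedule, accrual target, endpoints, data collection and interpretation are the same before and after the correction, so no change to the plan is called for. This rests on the protocol as shown, in which nothing ties study conduct to the size of this award.

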### Subject Information

*Target accrual is the proposed total number of subjects to be included in this study at Mayo Clinic. A "Subject" may include medical records, images, or specimens generated at Mayo Clinic and/or received from external sources.*

Target accrual: 10

Subject population (children, adults, groups): Participants will be men only requiring treatment for ED and following the inclusion/exclusion criteria below.

#### Inclusion Criteria:

1. The patient must have given his informed and signed written consent
2. The patient is a male
3. Between 40 to and including 55 years of age
4. The patient has ED for longer than 1 year but less than 5 years.
5. The patient is PDE5i responsive, meaning he is able to achieve and maintain an erection under the effect of the maximal dosage of PDE5i
6. IIEF-EF Domain score of 17-20
7. Evidence Based Criteria: Doppler Clinical Exam

#### Exclusion Criteria:

1. The patient is participating in another study that may interfere with the results or conclusions of this study
2. History of radical prostatectomy or extensive pelvic surgery
3. Past radiation therapy of the pelvic region within 12 months prior to enrollment
4. Recovering from cancer within 12 months prior to enrollment
5. Neurological disease which effects erectile function
6. Psychiatric disease which effects erectile function

7. The patient is taking blood thinners
8. History of Diabetes Mellitus
9. History of Coronary Artery Disease
10. Evidence Based Criteria: Doppler Clinical Exam
11. Severe erectile dysfunction with IIEF-EF domain score  $\leq 16$

### Research Activity

Check all that apply and complete the appropriate sections as instructed.

1.  **Drug & Device:** Drugs for which an investigational new drug application is not required. Device for which (i) an investigational device exemption application is not required; or the medical device is cleared/approved for marketing and being used in accordance with its cleared/approved labeling. (Specify in the Methods section)
2.  **Blood:** Collection of blood samples by finger stick, heel stick, ear stick, or venipuncture.
3.  **Biological specimens other than blood:** Prospective collection of human biological specimens by noninvasive means that may include: urine, sweat, saliva, buccal scraping, oral/anal/vaginal swab, sputum, hair and nail clippings, etc.
4.  **Tests & Procedures:** Collection of data through noninvasive tests and procedures routinely employed in clinical practice that may include: MRI, surface EEG, echo, ultrasound, moderate exercise, muscular strength & flexibility testing, biometrics, cognition testing, eye exam, etc. (Specify in the Methods section)
5.  **Data** (medical record, images, or specimens): Research involving use of existing and/or prospectively collected data.
6.  **Digital Record:** Collection of electronic data from voice, video, digital, or image recording. (Specify in the Methods section)
7.  **Survey, Interview, Focus Group:** Research on individual or group characteristics or behavior, survey, interview, oral history, focus group, program evaluation, etc. (Specify in the Methods section)

NIH has issued a *Certificate of Confidentiality (COC)*. When checked, provide the institution and investigator named on the COC and explain why one was requested. \_\_\_\_\_

### Review of medical records, images, specimens – Category 5

**For review of existing data:** provide a date range or an end date for when the data was generated. The end date can be the date this application was submitted to the IRB. Example: *01/01/1999 to 12/31/2015* or all records through *mm/dd/yyyy*.

**Date Range:** Prospective Pilot Investigation

**HIPAA Identifiers and Protected Health Information (PHI)**

Protected health information is medical data that can be linked to the subject directly or through a combination of indirect identifiers.

Recording identifiers (including a code) during the conduct of the study allows you to return to the medical record or data source to delete duplicate subjects, check a missing or questionable entry, add new data points, etc. De-identified data is medical information that has been stripped of all HIPAA identifiers so that it cannot be linked back to the subject. De-identified data is **rarely** used in the conduct of a research study involving a chart review.

**Review the list of subject identifiers below and, if applicable, check the box next to each HIPAA identifier being recorded at the time of data collection or abstraction.** Identifiers apply to any subject enrolled in the study including Mayo Clinic staff, patients and their relatives and household members.

**Internal** refers to the subject’s identifier that will be recorded at Mayo Clinic by the study staff.

**External** refers to the subject’s identifier that will be shared outside of Mayo Clinic.

Check all that apply:	INTERNAL	EXTERNAL
Name	X	
Mayo Clinic medical record or patient registration number, lab accession, specimen or radiologic image number	X	
Subject ID, subject code or any other person-specific unique identifying number, characteristic or code that can link the subject to their medical data	X	
Dates: All elements of dates [month, day, and year] directly related to an individual, their birth date, date of death, date of diagnosis, etc. Note: Recording a year only is not a unique identifier.	X	
Social Security number		
Medical device identifiers and serial numbers		
Biometric identifiers, including finger and voice prints, full face photographic images and any comparable images		
Web Universal Resource Locators (URLs), Internet Protocol (IP) address numbers, email address		
Street address, city, county, precinct, zip code, and their equivalent geocodes		
Phone or fax numbers		
Account, member, certificate or professional license numbers, health beneficiary numbers		
Vehicle identifiers and serial numbers, including license plate numbers		
Check ‘None’ when none of the identifiers listed above will be recorded, maintained, or shared during the conduct of this study. (exempt category 4)	 None	 None

**Data Analysis**

*Power analyses and study endpoints are not required for minimal risk research, pilot, nor feasibility studies.*

This investigation is a pilot study to determine the efficacy of the shockwave therapy MoreNova for patients with ED and as such, no previous formal power calculations were completed.

**Primary Endpoint:**

- To assess efficacy for patients receiving MoreNova therapy for treatment of ED via CDDU exam. To provide and evidence basis for improved of ED, we will closely monitor the 10 patients enrolled in the study. By including CDDU imaging done as part of patient's clinical assessment in PI's standard clinical practice, at time of last protocol treatment, and at 3-4 month follow-up, we will have evidence based data for improvement of erectile function. Specifically, we will measure cavernosal artery inflow, peak systolic velocity, end diastolic velocity, resistive index and erection hardness (EHS). CDDU is performed in privacy with Male Nurse provider recording Doppler data and PI performing ultrasound. Patients receive an intracavernous injection of alprostadil (10 mcg, standard of care). CDDU measurements are taken at 5-10 minutes and again after a period of privacy and visual sexual self-stimulation.

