#### APPROACH

This is prospective, pilot clinical study of 10 men aimed to evaluate the efficacy of MoreNova Shockwave therapy for men diagnosed with ED. We will restrict our target population to include men only between and including the ages of 40 and 55 who have been diagnosed with ED for over a year, but less than 5 years.

*Efficacy* is to be assessed by CDDU imaging during and from treatment up to follow-ups.

*Efficacy* is to be assessed by patient reported questionnaires data via IIEF-EF, SEP 2+3, GAQ and EHS that catalog the frequency of successful erections and side effects during treatment.

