#### RECRUITMENT

Review of clinic patient records within the MCF Department of Urology to identify potential research participants (patients with ED who have already presented to MCF and had initial evaluation and CDDU diagnosis). Participants will first be identified through the treating physician and the PI on this proposal, [name]. The study coordinator will then be notified of the potentially eligible patient who will further screen for eligibility. Once the patient has been determined eligible, the study coordinator will contact the potential study participant to schedule a research appointment to discuss the study in detail. The study coordinator will meet with the patient, describe the goals of the study, and ask if they would like to participate. If the patient agrees to participate at this time, a signed Patient Informed Consent is obtained before the patient leaves. The patient can decide at a later date to sign Informed Consent. If so, the study coordinator will schedule an appointment at a time when the patient will return for an appointment with a consultant. Recruitment will take place in quiet room where the study will be explained fully and the patient will have adequate time to decide. If a patient declines consent, the study coordinator will express that this in no way affects their current or future medical care.

Given the paperless initiative put forth by the clinical studies units, this study will utilize the Research Participant Tracking (PTrax) digital signature capture feature.

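### The PI performs the ultrasound exams behind the primary endpoint, and nothing keeps earlier values out of view, so a measurement shift would enter the estimated change in full

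*Protocol*

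**What the plan says.** The protocol's APPROACH section describes the design: "This is prospective, pilot clinical study of 10 men aimed to evaluate the efficacy of MoreNova Shockwave therapy". One group is treated; no comparator, randomisation or masking is described.

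The Primary Endpoint section lists the measurements: "we will measure cavernosal artery inflow, peak systolic velocity, end diastolic velocity, resistive index and erection hardness (EHS"). It also assigns the roles in the CDDU exam: "Male Nurse provider recording Doppler data and PI performing ultrasound". The baseline is "CDDU imaging done as part of patient's clinical assessment in PI's standard clinical practice".

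The PARTICIPATION section says that the baseline CDDU will "be reviewed in clinical records (within 12 months prior to study enrollment"), and on the later exams it says: "CDDU will be repeated as part of the study at the final treatment and at the 3-4-month follow-up".

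On who knows the men beforehand, the RECRUITMENT section states: "Participants will first be identified through the treating physician and the PI on this proposal".

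No section mentions withholding earlier CDDU values from the operator, storing tracings, a coded re-read, a second reader or a repeatability check.

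**The concern.** Peak systolic velocity, end diastolic velocity and resistive index depend on which waveform the operator selects and how it is measured, and erection hardness is a rating. The person performing the exam knows that the man has been treated. At the sixth treatment he also knows the visit, because the exam and the treatment fall together. He is free to look at the earlier result before he measures.

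In a controlled trial with a masked operator, a drift or expectation effect would fall on both groups and largely cancel. Here there is one group, so whatever systematic difference exists between baseline and follow-up measurement is added to the estimated change. This matters because the protocol presents CDDU as the evidence-based counterpart to the patient questionnaires and states efficacy as its purpose. The primary endpoint's value rests on its being more objective than self-report.

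**Working it through.** **What is fixed and what is inferred**

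- Operator: the Primary Endpoint section names the PI as performing the ultrasound and a nurse as recording. It names no separate reader. That the PI also selects and measures the waveforms is a reasonable inference, not a stated fact.
- Baseline: it comes from the PI's standard practice. Who held the probe is not stated.
- Follow-up exams: two per man, at treatment 6 and at 3-4 months. With the baseline, that is 10 × 3 = 30 exams at most.
- Safeguards: none described.

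**How large a shift would matter**

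The protocol states no test, alpha, SD or reader repeatability, and the Data Analysis section says that no power calculation was done. There is therefore no figure of the plan's own to reproduce. What follows is an illustration under assumptions: a paired t-test on the change, n = 10, two-sided alpha 0.05, true change zero, and a constant measurement shift of d standard deviations of the change.

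1. Critical value: t(0.975, 9 df) = 2.262.
2. 95% confidence interval half-width for the mean change: 2.262 / √10 = 0.715 SD. An observed mean change of about 0.72 SD is enough for p < 0.05.
3. With shift d, the test statistic follows a noncentral t distribution with 9 df and noncentrality d × √10. The rejection rate is the probability of falling beyond ±2.262.

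| Shift d (assumed) | d × √10 | Significant improvement | Either direction |
|---|---|---|---|
| 0 | 0 | 2.5% | 5.0% |
| 0.1 | 0.316 | 4.7% | 5.9% |
| 0.25 | 0.791 | 10.6% | 10.9% |
| 0.5 | 1.581 | 29.3% | 29.3% |

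The rates are per measure. A shift of 0.25 SD is 0.25 / 0.715 = 35% of the half-width; a shift of 0.5 SD is 70% of it.

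A small shift does little harm and a moderate one does a good deal. The protocol offers no means of telling which applies.

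**The case against.** - **It is an unpowered 10-man pilot.** That excuses the absence of a power calculation. It does not remove the value of an inexpensive safeguard when the stated aim is efficacy. It does limit how much weight the point carries.
- **The shift sizes have no source.** This stands. Any constant bias of the same size would give the same rates, so the table shows sensitivity and is not evidence that reader bias is present.
- **The nurse records the data.** Recording does not mask the person who chooses the waveform.
- **The analysis plan could deal with it.** Who scans, what they see beforehand and whether tracings are kept are matters of conduct, and the protocol already names the operator. A tracing that was not saved cannot be re-read later.
- **Masking is impractical.** This stands for acquisition: the visit cannot be hidden at treatment 6, and part of the choice of waveform happens during the scan. The PI may also have seen the baseline when identifying the man, so keeping earlier results closed gives only partial masking.
- **No other staff are shown to be able to measure Doppler tracings.** This stands. The coordinator, the research assistant and the staff giving the therapy are described in other roles. A coded re-read may therefore have to be done by the PI.
- **Partial re-reading could add bias.** This also stands. If follow-up tracings were re-read under code but some baselines were not, the change score would combine two kinds of measurement. The remedy has to rule that out.

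A reader might infer that the PI personally performed and read every exam including the baseline, or that existing staff could mask the whole procedure. The protocol supports neither. It names the PI as operator and identifies his practice as the source of the baseline, but does not say who did or read that scan, and it describes no other qualified reader.

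**Conclusion.** The point holds as an inexpensive improvement to the conduct of the primary endpoint. The PI performs the exams that supply it, no other reader is named, all 10 men are treated, and nothing prevents sight of earlier values. A systematic shift would enter the estimated change in full.

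The size is conditional. Under the assumed test and alpha, the false-positive rate lies between about 6% and 29% for shifts of 0.1 to 0.5 SD, and the protocol does not say where in or outside that range the real shift lies. The documents do not show that such a shift will occur.

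**What to change.** Add to the Primary Endpoint section:

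1. At each study CDDU, the PI and the nurse do not open earlier CDDU results until the current values have been recorded and locked.
2. The study tracings are saved. After the last 3-4-month visit they are re-measured once, with patient and date hidden and in random order, by the PI if no other study staff member is qualified.
3. The coded re-read is used for the change from baseline only in men whose baseline tracing is also stored and re-read in the same way. For all 10 men, the change is reported from the values recorded at the exam. Coded and uncoded readings are never combined within one change score.

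**Cost:** protocol wording, image storage and a few hours of existing staff time for at most 30 exams. Treatment, visits and sample size do not change.

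**Limits:** acquisition stays unmasked, the PI may already know the baseline from screening, and some baselines may have no stored tracing. The lack of a control group and regression to the mean are untouched.
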